3.6.1.1 Sensitivity Analysis

ANCOVA (analysis of covariance) model will be conducted with the olanzapine lead-in period weight change strata and treatment group as factor and the baseline weight as the covariate for FAS 1. The ANCOVA model will be based on the LOCF (last observation carried forward) imputation, that is, if a subject misses a post-baseline scheduled visit, a record for the scheduled visit will be imputed using the value from the most recent post-baseline visit.

For both FAS 1 and FAS 2 populations, summary of change from baseline in PANSS total score and subscales at each visit will also be presented using descriptive statistics. Change from Part B baseline will also be summarized at each visit in Part B.

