2 SAMPLE SIZE CONSIDERATIONS

Sample size calculations are based on the primary endpoint of absolute change in PANSS total score. These calculations assume an equivalence margin of 10 points, a standard deviation of 20 points, and a true difference of 0 points. With these assumptions, 280 randomized subjects provide 95% power to demonstrate equivalence on the primary endpoint (absolute PANSS total score change from randomization to the end of Part A) with a 2-sided test at an alpha level of 0.05. These 280 subjects represent 70 subjects for each treatment arm (ALKS 3831 5 mg, ALKS 3831 10 mg, ALKS 3831 20 mg, and placebo) in a 1:1:1:1 ratio. For the primary analysis, subjects in the 3 ALKS 3831 treatment groups will be pooled for comparison with placebo. If this analysis shows equivalence, follow-up analyses on individual dose levels will be performed. Assuming a 20% discontinuation rate prior to randomization, an estimated 350 subjects will be enrolled in this study.

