3.4 DEMOGRAPHICS AND BASELINE CHARACTERISTICS

Demographics and baseline characteristics such as gender, age, race, ethnicity, weight, BMI, PANSS, and CGI-S will be summarized by treatment group and overall for FAS 1 Population, FAS 2 Population, and Safety Population.

If there are heterogeneities between treatment groups in any of the subject characteristics that are of clinical importance or could affect the treatment outcome, the impact of the imbalances will be investigated and, if necessary, appropriate adjustments will be considered in the efficacy and safety analyses.

Medical and psychiatric history will be summarized by treatment group and overall using the number and percentage of subjects by category for the Safety Population.

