3.6 EFFICACY ANALYSIS

3.6.1 Change in PANSS total Score

The primary endpoint is the change in PANSS total score from randomization to Day 92 and will be evaluated by treatment group (ALKS 3831 pooled vs. the placebo group [olanzapine alone]) using a 2-sided mixed-model for repeated measures (MMRM) to test for equivalence at an alpha level of 0.05. The primary analysis will be conducted in the FAS 1 population.

The null hypothesis is that the PANSS total score change from randomization to Day 92 of ALKS 3831 treatment group will be different to that of the placebo group [olanzapine alone]. The bound of the 2-sided 95% CIs of the difference between the changes of ALKS 3831 – Placebo [olanzapine alone] will be outside the equivalence interval of -10 and 10.

If this analysis shows equivalence, similar analyses on individual dose levels will be performed.

Change in PANSS total score from baseline to Day 92 will be analyzed using MMRM model. The MMRM model will include variables for weight change strata in the olanzapine lead-in period, treatment group, visit, and treatment group-by-visit interaction term as categorical fixed effect, baseline value will be included as a covariate. An AR(1) covariance structure will be

applied for the MMRM. The Kenward-Roger approximation [2] will be used to adjust the denominator degree of freedom. The analysis will be performed on all observed post-randomization scores without imputation of missing data.

A sample of SAS implementation code for analyzing change from randomization to Day 92 using an MMRM is given below.

```
proc mixed data=datain;  
class strata usubjid trt visit;  
  model change = strata trt visit trt*visit base  
    / DDFM=KENWARDROGER;  
repeated visit/ type=AR(1) subject=usubjid;  
lsmeans trt*visit / diff cl;  
run;
```

The least squares (LS) mean, standard error (SE), and LS mean difference between pooled ALKS 3831 treatment group and placebo [olanzapine alone], as well as between each ALKS 3831 treatment group and the placebo [olanzapine alone] at Day 92, along with the 95% CI, will be summarized.

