3.6.2 Percent Change in Body Weight

The secondary endpoint, percent change in weight from randomization to Day 92, will be evaluated by treatment group using an MMRM approach similar to that of the primary endpoint. Pooled and individual ALKS 3831 treatment group will be compared to the placebo [olanzapine alone] group with a 2-sided hypothesis test to test for superiority at an alpha level of 0.05. The secondary efficacy analysis will be conducted in both FAS 1 and FAS 2 population. The MMRM model includes variables for the weight change strata in olanzapine lead-in period, treatment group, visit, and treatment group-by-visit interaction term as categorical fixed effect; baseline weight value will be included as a covariate.

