3.6.2.1 Sensitivity Analysis

To assess the robustness of the MMRM results on the percent weight change, ANCOVA and LOCF analysis will be conducted with the olanzapine lead-in period weight change strata and treatment group as factor and the baseline weight as the covariate (similar as Section 3.6.1.1).

In addition, the MMRM model will include treatment group, visit, and treatment group-by-visit interaction term as categorical fixed effect; baseline BMI value and continuous weight change value in the olanzapine lead-in period will be included as covariates.

Percent weight change will also be analyzed by a linear mixed effects model with treatment as fixed effect, visit and treatment by visit interaction as random effect, and with adjustment for the olanzapine lead-in period weight change strata as factor and baseline weight as covariates. In this model, visit will be treated as a continuous variable and will be the number of days from Day 8. Denominator degrees of freedom will be estimated using the Kenward–Roger approximation. Change from baseline at Day 92 will be obtained from the model.

For both FAS 1 and FAS 2 populations, summary of weight change from baseline at each visit will also be presented using descriptive statistics for both Part A and Part B. Change from Part B baseline will also be summarized at each visit in Part B.

Waterfall plots will be produced for the percent change from baseline to Day 92 by the treatment group.

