3.6.6 Change in Clinical Global Impression - Severity

The CGI-S is a 7-point scale ranging from 1=normal to 7=extremely ill. .

The change from baseline to Day 92 in CGI-S will be carried out using the MMRM model including the weight change strata in olanzapine lead-in period, treatment group, visit, and a treatment group-by-visit interaction term as categorical fixed effects; baseline CGI-S value will be included as a covariate.

A summary of CGI-S at each visit will be presented using descriptive statistics for Part A and Part B.

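### The PANSS sensitivity ANCOVA adjusts for baseline body weight instead of baseline PANSS, so it changes the covariate along with the missing-data method

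*SAP*

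**What the plan says.** SAP 3.6.1.1 belongs to the section on change in PANSS total score. It specifies an ANCOVA with "the olanzapine lead-in period weight change strata and treatment group as factor and the baseline weight as the covariate for FAS 1", and adds: "The ANCOVA model will be based on the LOCF (last observation carried forward) imputation". No baseline PANSS term is listed.

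The models around it do otherwise:

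- **3.6.1, primary PANSS MMRM:** "baseline value will be included as a covariate". The sample code enters it as a single term for the baseline of the analysed variable. The model uses observed scores without imputation.
- **3.6.2, weight MMRM:** "baseline weight value will be included as a covariate".
- **3.6.6, CGI-S MMRM:** "baseline CGI-S value will be included as a covariate".
- **3.6.7, waist circumference MMRM:** the outcome's own baseline value.
- **3.6.2.1, weight ANCOVA:** almost the same sentence as 3.6.1.1, ending "treatment group as factor and the baseline weight as the covariate (similar as Section 3.6.1.1". Here baseline weight is the outcome's own baseline.

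The SAP gives no reason for using body weight in a PANSS model. The protocol does not specify this ANCOVA.

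**The concern.** A sensitivity analysis is informative when it varies one assumption and holds the rest as close to the primary analysis as it can. This one is meant to show whether the PANSS result depends on how missing scores are handled. Because the covariate changes too, a disagreement with the MMRM cannot be put down cleanly to missing data.

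There are two further costs. A baseline score usually explains part of the variance in change, so leaving it out loses precision. A chance imbalance in baseline PANSS also goes straight into the estimated difference in change. This matters more because it is the only other inferential PANSS model in the SAP; the remainder of 3.6.1.1, including FAS 2, is descriptive.

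**Working it through.** **Inputs.** From SAP section 2: margin 10, "a standard deviation of 20 points, and a true difference of 0 points", 70 subjects per arm, three active arms pooled (210 against 70). From SAP 3.6.1: a two-sided 95% CI judged against -10 to 10. Assumed, because the documents do not give them: baseline PANSS SD of 10, slope of change on baseline from -0.3 to -1.0, complete data.

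**Reproducing the plan's figure.** SE = 20 × √(1/210 + 1/70) = 2.76. Power for equivalence at a true difference of 0 is 2Φ(10/2.76 − z) − 1. With z = 1.645 (90% CI) this is 95.2%, which matches the stated 95%. With z = 1.96 (the 95% CI rule in 3.6.1) it is 90.4%. That mismatch is a separate matter; here the calculation only confirms the SE.

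**Precision.** The correlation is r = |slope| × 10/20. The 95% half-width without baseline PANSS is 1.96 × 2.76 = 5.41 points. With baseline PANSS it is 5.41 × √(1 − r²), so leaving it out widens the CI by the factor 1/√(1 − r²).

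**Chance imbalance.** The SE of the baseline difference is 10 × √(1/210 + 1/70) = 1.38 points. An imbalance of k SEs shifts the unadjusted estimate by k × 1.38 × |slope|. An imbalance of 2 SEs or more occurs in about 1 trial in 20.

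**Simulation.** 8,000 trials per value of r, true difference 0, model without against model with baseline PANSS.

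| Slope | r | CI widening factor | Adjusted half-width | 1-SE shift | 2-SE shift | Equivalence shown, without / with | Verdicts differ |
|---|---|---|---|---|---|---|---|
| -0.3 | 0.15 | 1.011 | 5.35 | 0.41 | 0.83 | 90.3% / 90.9% | 2.2% |
| -0.5 | 0.25 | 1.033 | 5.24 | 0.69 | 1.38 | 90.1% / 92.0% | 4.1% |
| -0.6 | 0.30 | 1.048 | 5.16 | 0.83 | 1.66 | 90.2% / 93.0% | 5.0% |
| -1.0 | 0.50 | 1.155 | 4.69 | 1.38 | 2.76 | 89.8% / 97.2% | 8.2% |

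Mean estimates were within 0.05 of zero in both models, so there is no bias.

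These runs had no weight term. Further runs of 4,000 trials put a weight covariate unrelated to PANSS change in the model and compared it with baseline PANSS. The two estimates differed with an SD of 0.86 points at r = 0.3 and about 1.4 points at r = 0.5. Verdicts differed in 2.9%, 5.1% and 9.1% of trials at r = 0.15, 0.3 and 0.5, which agrees with the table within simulation error. Strata and dropout were not simulated.

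**The case against.** The strongest reply is that little depends on this model. SAP 3.6.1.1 gives it no hypothesis, margin or gatekeeping role. The equivalence conclusion and the step to individual doses rest on the MMRM, which does adjust for baseline PANSS. On average the error is conservative, since omitting baseline PANSS makes equivalence slightly harder to show. All of this stands, and it limits the consequence.

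Second, the fix does not make the comparison clean. Moving from an AR(1) repeated-measures model to an ANCOVA on LOCF data also changes the model form. That is true, but it comes with the chosen method, whereas the covariate swap is avoidable.

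Third, the upper figures are extreme. A slope of -1.0 with a baseline SD of 10 gives a covariance between baseline and Day 92 scores of 100 − 100 = 0, meaning that baseline says nothing about the later score. That is hard to defend in the clinically stable subjects of Protocol 7.1. The r = 0.15 to 0.30 rows are the more reasonable guide.

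Fourth, SAP 3.4 lists PANSS among the baseline characteristics and says that, if groups differ, "appropriate adjustments will be considered in the efficacy and safety analyses". That is discretionary and comes after inspection of the data, so it does not replace a pre-specified covariate. Protocol 14.4 plans a repeat of the primary analysis in FAS 2 where applicable, but that is a different population, and the SAP gives no inferential PANSS model for it.

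**Conclusion.** The concern holds. As written, the only alternative inferential model for the primary endpoint leaves out the outcome's own baseline and uses a covariate that belongs to another endpoint. That this is a carry-over from 3.6.2.1 is an inference from the matching wording; the mismatch does not depend on it.

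The size is modest. For r of 0.15 to 0.30 the CI is about 1% to 5% wider, a 2-SE baseline imbalance moves the estimate by 0.8 to 1.7 points against a margin of 10, and the covariate alone changes the verdict in about 2% to 5% of trials. At the extreme of r = 0.5 these become 15%, 2.8 points and 8%. The figures rest on the assumed baseline SD and slopes, complete data, and body weight being unrelated to PANSS change. If weight were related to it, the SAP's model would recover some of the lost precision.

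This should be corrected, but it does not threaten the primary analysis.

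**What to change.** In SAP 3.6.1.1, replace *baseline weight* with *baseline PANSS total score* and keep the lead-in strata and treatment group as factors. If body weight was intended, add baseline PANSS as well and give the reason for weight.

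Two optional edits would help. State in 3.6.1.1 that the Day 92 difference is read against the same -10 to 10 interval as the primary analysis. In 3.6.2.1, limit the cross-reference to the LOCF method, so that the weight ANCOVA clearly keeps baseline weight.

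The cost is one phrase, plus a cross-reference if wanted. PANSS is already scheduled at Visit 3 (Protocol Table 1), so no new data are needed. The change should be made before unblinding, so that the covariate is not chosen with results in view.

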3.6.2 Percent Change in Body Weight

The secondary endpoint, percent change in weight from randomization to Day 92, will be evaluated by treatment group using an MMRM approach similar to that of the primary endpoint. Pooled and individual ALKS 3831 treatment group will be compared to the placebo [olanzapine alone] group with a 2-sided hypothesis test to test for superiority at an alpha level of 0.05. The secondary efficacy analysis will be conducted in both FAS 1 and FAS 2 population. The MMRM model includes variables for the weight change strata in olanzapine lead-in period, treatment group, visit, and treatment group-by-visit interaction term as categorical fixed effect; baseline weight value will be included as a covariate.

3.6.2.1 Sensitivity Analysis

To assess the robustness of the MMRM results on the percent weight change, ANCOVA and LOCF analysis will be conducted with the olanzapine lead-in period weight change strata and treatment group as factor and the baseline weight as the covariate (similar as Section 3.6.1.1).

In addition, the MMRM model will include treatment group, visit, and treatment group-by-visit interaction term as categorical fixed effect; baseline BMI value and continuous weight change value in the olanzapine lead-in period will be included as covariates.

Percent weight change will also be analyzed by a linear mixed effects model with treatment as fixed effect, visit and treatment by visit interaction as random effect, and with adjustment for the olanzapine lead-in period weight change strata as factor and baseline weight as covariates. In this model, visit will be treated as a continuous variable and will be the number of days from Day 8. Denominator degrees of freedom will be estimated using the Kenward–Roger approximation. Change from baseline at Day 92 will be obtained from the model.

For both FAS 1 and FAS 2 populations, summary of weight change from baseline at each visit will also be presented using descriptive statistics for both Part A and Part B. Change from Part B baseline will also be summarized at each visit in Part B.

Waterfall plots will be produced for the percent change from baseline to Day 92 by the treatment group.

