3.6.3 Absolute Change in Body Weight

The statistical analysis for absolute change in weight will be similar to the analysis for percent change in body weight (Section 3.6.2).

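### The mixed-model check of percent weight change has no fixed time term, so its treatment contrast cannot give the Day 92 result, and no other route is stated

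*SAP*

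**What the plan says.** SAP 3.6.2.1 lists several checks on the MMRM for percent weight change. The one at issue is a "linear mixed effects model with treatment as fixed effect, visit and treatment by visit interaction as random effect", "with adjustment for the olanzapine lead-in period weight change strata as factor and baseline weight as covariates". It adds that "visit will be treated as a continuous variable and will be the number of days from Day 8", so Day 92 corresponds to t = 92 - 8 = 84. On inference it says "Denominator degrees of freedom will be estimated using the Kenward–Roger approximation". On the result it says only "Change from baseline at Day 92 will be obtained from the model".

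For this model the SAP gives no contrast, prediction step, grouping level for the random terms, covariance structure or code.

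The neighbouring models treat the same two terms differently. The main weight MMRM in SAP 3.6.2 has "treatment group, visit, and treatment group-by-visit interaction term as categorical fixed effect; baseline weight value will be included as a covariate". The BMI-adjusted version in 3.6.2.1 says "the MMRM model will include treatment group, visit, and treatment group-by-visit interaction term as categorical fixed effect; baseline BMI value". Both therefore yield a Day 92 difference directly.

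**The concern.** A treatment effect on weight gain should grow from about zero at Day 8. To express that growth on average, a model needs a fixed time term and a fixed treatment-by-time term. This model puts both in the random part, where their means are zero by definition. Its fixed part is then constant over time in each arm, and so is the difference between arms.

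The plan leaves at least four ways to produce a Day 92 figure: report the treatment coefficient, average the subject-level predictions, fit arm-level random slopes, or add the fixed terms without saying so. They give different answers or different standard errors. Reporting the coefficient could make the check appear to contradict a sound MMRM result. Averaging predictions could give a reasonable estimate with far too narrow an interval. A pre-specified robustness check should not leave that choice open.

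**Working it through.** The plan gives no figure to reproduce here. Its sample size rests on PANSS, and it states no expected weight change, weight SD or post-randomization dropout. The first step below needs no assumed number; the rest are illustrations under stated assumptions.

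**1. Algebra.** With mean-zero random terms,

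E[Y | arm, t] = intercept + arm effect + stratum + baseline weight.

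There is no t on the right, so the arm contrast at t = 84 equals the contrast at t = 1. If the random terms are at subject level, each subject has one treatment. With a common variance for each term, the covariance then depends only on the sum of the visit and treatment-by-visit slope variances, so the two cannot be separated.

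**2. What the treatment coefficient estimates.** Weight is measured at Visits 4 to 13 (protocol Table 1), so t = 1, 2, 7, 14, 21, 28, 42, 56, 70, 84. Let u = t/84, let c be the shape of the true difference (c = 1 at Day 92), and let V = τ²uu′ + σ²I. The share of the Day 92 difference recovered is (1′V⁻¹c)/(1′V⁻¹1). Here τ² = slope SD² + mean gain², because no fixed slope absorbs the mean gain. A random intercept would not change this share, since adding a multiple of 11′ to V leaves the weights for a constant unchanged.

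For a linear difference (c = u) it reduces to

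σ²S₁ / [nσ² + τ²(nS₂ - S₁²)],

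with n = 10, S₁ = 325/84 = 3.869 and S₂ = 18331/7056 = 2.598, so nS₂ - S₁² = 25.98 - 14.97 = 11.01.

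Assumed grid, in percentage points at Day 92: slope SD 2-5, mean gain 2-3, residual SD 0.7-1.5.

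- Low end (slope SD 5, gain 3, σ 0.7): τ² = 34 and σ² = 0.49, giving 1.896/(4.9 + 374.3) = 0.005.
- High end (slope SD 2, gain 2, σ 1.5): τ² = 8 and σ² = 2.25, giving 8.705/(22.5 + 88.1) = 0.079.

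Shares over the grid, by shape of the true difference:

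| Shape | All ten weight days | Visits 6-13 only |
|---|---|---|
| Linear | 0.5-8% | 0.9-13% |
| Saturating, 42-day constant | 13-20% | 22-32% |
| Square root | 22-28% | 30-39% |
| Saturating, 21-day constant | 25-32% | 42-50% |

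**3. Simulation of the possible routes.** Assumptions: 70 placebo and 210 pooled active subjects (allocation from SAP section 2), mean gains of 4% and 2% at Day 92 (true difference -2.0), subject-level random slope, 300 datasets per scenario, REML, normal 95% intervals, no strata or baseline-weight terms. Monte Carlo error on each mean prediction is about 0.55/√300 = 0.03. Results without dropout:

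| Slope SD, residual SD | Shape | Treatment coefficient | Averaged predictions at t = 84 | Coverage of prediction interval | Fixed day and treatment-by-day |
|---|---|---|---|---|---|
| 4, 0.7 | Linear | -0.01 | -1.94 | 18% | -1.96 |
| 4, 0.7 | Square root | -0.44 | -2.14 | 17% | -2.16 |
| 4, 0.7 | 21-day | -0.51 | -2.34 | 11% | -2.37 |
| 3, 1.5 | Linear | -0.09 | -1.89 | 46% | -2.04 |
| 3, 1.5 | Square root | -0.51 | -2.00 | 49% | -2.14 |
| 3, 1.5 | 21-day | -0.59 | -2.23 | 43% | -2.38 |

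The low coverage has a simple cause. The prediction-error SE (0.06-0.14) takes these subjects' own slopes as the target and leaves out between-subject sampling. That omitted part is slope SD × √(1/70 + 1/210) = slope SD × 0.138, which is 0.55 for SD 4 and 0.41 for SD 3. The observed sampling SD was 0.39-0.56.

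**4. Dropout.** Linear trend, random dropout, last weight uniform over the Day 15-78 visits. A subject with few visits has a predicted slope pulled towards zero, not towards the arm mean.

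| Dropout | Slope SD, residual SD | Averaged predictions | Fixed-term model |
|---|---|---|---|
| 20% | 4, 0.7 | -1.94 | -2.06 |
| 20% | 3, 1.5 | -1.67 | -1.99 |
| 40% | 4, 0.7 | -1.86 | -2.07 |
| 40% | 3, 1.5 | -1.49 | -1.97 |

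Under the linear trend, with and without dropout, the fixed-term model's interval covered -2.0 in 92-96% of datasets.

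**5. Arm-level reading.** If the random slopes were meant per arm with no subject term, the model SE of the Day 92 difference is about 0.20, against a true 0.56 (SD 4) or 0.44 (SD 3).

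**The case against.** The strongest reply is that this is loose drafting of an ordinary random-slope model. Coding visit in days and promising a Day 92 value suggests evaluating the model at t = 84, and naming Kenward-Roger suggests inference on fixed terms. The SAP nowhere says that the treatment coefficient will be reported, and it speaks of a change at Day 92, not of a difference. Averaged predictions do recover a Day 92 value, and in all four front-loaded cases above they lie closer to -2.0 than the fixed-term model does. The poor coverage belongs to a procedure and an SE that the SAP does not specify.

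Much of this is fair. The 0.5-50% recovery applies only if the coefficient is reported. All weight inputs are assumed. A straight-line fixed model overstated front-loaded effects by 7-19%, with coverage of 87-89% in the 21-day cases.

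It does not remove the point. The text says random where the neighbouring MMRMs say fixed, so the written specification is wrong and not merely brief. The per-arm change is as constant over time as the difference, and the check exists to test a between-arm result. Charity from the reader cannot replace a stated contrast, standard error and grouping level.

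**Conclusion.** The concern holds. That the treatment contrast is constant over time follows from the written model and rests on no assumption. The sizes rest on assumed weight gains, variances, trend shapes and random dropout. In those settings the coefficient recovers from almost nothing to about half of the Day 92 difference. Averaged predictions are close without dropout under a linear trend, but they shrink with dropout and carry an interval that is much too narrow.

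The consequence is limited. This is one sensitivity analysis of a secondary endpoint, and no alpha or decision rule depends on it. The main MMRM, the ANCOVA with LOCF and the BMI-adjusted MMRM are unaffected. It may extend to absolute weight change, since SAP 3.6.3 says "The statistical analysis for absolute change in weight will be similar to the analysis for percent change in body weight". That section points to 3.6.2 while this model sits in 3.6.2.1, so the extension is possible but not certain. It should be corrected, but it does not threaten the trial's conclusions.

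**What to change.** Replace the model sentence in SAP 3.6.2.1 with one that states:

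- fixed effects for treatment, day (continuous, from Day 8), treatment-by-day, lead-in stratum and baseline weight;
- a subject-level random intercept and random slope for day, with the covariance structure named;
- Day 92 difference = treatment + 84 × treatment-by-day, from the fixed effects, with its Kenward-Roger confidence interval.

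A fixed curvature term in day, with its treatment interaction, is optional. It would address the 7-19% overstatement seen with front-loaded effects, and the Day 92 contrast would then include those terms. SAP 3.6.3 should also say whether this check applies to absolute weight change.

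The cost is one SAP sentence and no new data.
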